## **COMPENSATION**

Patients were offered \$50 Target gift cards for completion of the baseline assessment to compensate them for their time. Patients were offered \$50 Target gift cards for completion of the 6-month and 12-month telephone assessment (\$150 possible total for all assessments).

## **VULNERABLE POPULATIONS**

We did not specifically exclude patients identified as vulnerable populations (e.g. educationally or economically disadvantaged patients). This was a low-risk behavioral study that did not include the use of any pharmaceuticals prescribed by the study. Participation in the study was completely voluntary, and patients could refuse. It was possible that some KP employees could be recruited. However, there was no coercion to participate and participation in the study had no impact on employment status or treatment.

## **RISKS AND BENEFITS**

This study entailed no physical procedures and imparted no physical risk. However, because materials for the study entailed disclosure about sensitive information, there were risks to confidentiality. Participants may have felt uncomfortable disclosing information about their chronic pain. In addition, it was expected that some individuals could receive a more effective treatment than others. Specifically, those assigned to the usual care group condition may not have experienced as much improvement in study outcomes as those assigned the experimental behavioral health intervention.

The experimental treatment in this study was a behavioral health intervention and was considered a low-risk treatment method. The intervention was conducted at the same treatment location where patients received usual care. [name] and [name] carefully monitored delivery of the intervention and took steps to ensure participant safety. Finally, all participants (participants in both treatment arms) received the same ongoing medical care in the KPNC health plan they would have received if they were not part of the study.

**Safety monitoring plan and reporting mechanisms.** In addition to the data security measures discussed, we utilized an Independent Safety Monitor (ISM) who periodically examined aggregate reports of adverse events generated by the primary data analyst. Risk to patients was extremely low relative to biomedical randomized controlled trials. The ISM did not have any personal or professional interest in the outcome of the trial.

The role of the ISM was to (1) monitor and evaluate the safety of study participants, (2) monitor the performance of the study, and (3) assure that the data safety and monitoring plan, including the reporting of any adverse events (AEs) and serious adverse events (SAEs) was adhered to.

We did not anticipate any injuries in the course of the study. For any potential injury, patients were eligible for services based on their usual KPNC health plan coverage. The PIs monitored the safety and efficacy of the study by compiling a data and safety monitoring report twice yearly and submitting it for review to the ISM. The report included a summary of all serious and non-serious adverse events, relationship to the intervention and recommendation for action.

**Study-specific potential adverse events.** There were no physical procedures to patients and risk of study-specific adverse events was very low. The study team members were trained to identify adverse

reactions. A study participant could be withdrawn from the study intervention if the investigator determined that it was the best decision in order to protect the safety of the member

**Procedures in case of clinical escalation during the study follow-up period.** Participants in the study had resources available to them through primary care as well as specialty care clinics within KPNC. All study participants were members of the KPNC health plan and were able to access services directly. Study interviewers were well trained and had KPNC and public telephone numbers and resources available in order to effectively link participants with clinical and emergency services if such need became apparent during course of the study. The investigators took all necessary steps to ensure patient safety, ensuring that participants received clinical attention and that participants were quickly evaluated by a provider in primary care, if these steps were needed. All participants received ongoing usual clinical care from primary care services.

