### **SIGNIFICANCE**

Chronic non-cancer pain is widespread and debilitating, often involving multiple chronic health conditions, and is a burden on patients, their families, and health systems. The Institute of Medicine's 2011 report, "Relieving Pain in America" estimated that roughly 100 million adult Americans suffer from chronic pain, a number which only stands to increase due to an aging population and increasing chronic disease. It is one of the most common complaints presenting in primary care, and costs the U.S. between \$560-635 billion annually in health care and lost productivity. We focused on chronic non-cancer pain, since clinical considerations differ for individuals with a terminal condition.

Patients with chronic pain (PWCP) can have considerable work and social disability, compromised quality of life, loss of function, and isolation from family and friends. PWCP suffer from social stigma as well, and frequently from depression. The impact on patients' family members and community is also considerable, as we learned in our prior surveys and recent qualitative work with PWCP.

Prescription opioids are the most common medication used to treat pain, and their use has increased dramatically in recent years. However, long-term use, or chronic opioid therapy (COT), remains controversial; and evidence supporting COT for long-term pain and functional outcomes is mixed. There is considerable evidence and concern over associated harms. Increases in adverse events such as opioid abuse, falls, overdose and deaths associated with COT has led to what has been called a prescription opioid epidemic. The overdose rate in 2008 was nearly four times the rate in 1999, with 14,800 prescription opioid overdose deaths. Hospitalizations for prescription opioid poisoning doubled from 1999 to 2006. From 2004 to 2009, emergency room visits involving prescription opioids nearly doubled. From 1999 to 2009, drug abuse treatment admissions rates for non-heroin opiates grew over 400%. In 2010, 11.1% of persons age 18-25 used prescription opioids non-medically, and 1.4% were prescription opioid dependent. Patients may be unaware of long-term risks.

Federal agencies and health systems are responding to the increased rates of mortality and overdose with new initiatives related to opioid prescribing. The Food and Drug Administration (FDA) has issued Risk Evaluation and Mitigation Strategies (REMS) for training and education materials for prescribers of

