*Prescription Opioid Use.* Pharmacy data on opioid dispensations were extracted and summarized from the EHR. We asked about patients' long-term goals for prescription opioid use among 4 categories: stay the same, increase, decrease, and stopping. Progress toward goals was assessed at 6 and 12 month follow-ups.

*Pain Management.* The survey asks questions about non-pharmaceutical pain management strategies.

*Opioid Misuse.* The Screener and Opioid Assessment for Patients in Pain (SOAPP) and Current Opioid Misuse Measure (COMM) were used to identify aberrant behaviors related to long-term opioid treatment.

*Other (non-opioid) Substance Use.* Drug, alcohol and tobacco use were collected from patient survey data.

*Health Care Utilization and Engagement.* Primary care services (number of non-urgent outpatient visits) and acute care services (number of emergency room visits and inpatient stays) within KPNC were extracted from the EHR. Questions on services received outside KPNC were included in the patient survey. Use of Kaiser's patient portal and health education programs were extracted from EHR and assessed by self-report.

**Patient Activation Group Intervention Sessions Curriculum.** The intervention consists of 4 group sessions, one meeting per week, led by a licensed psychologist trained in pain management.

Session 1: "Taking a Leading Role". This session focused on empowering patients to take a leading role in their pain management and overall healthcare. It provides patients with information about how pain manifests in the brain and the body via the Gate Control Theory of Pain, the long-term risks and side effects of prescription opioid use and how neuroplasticity can cause pain to become chronic in nature and render pain medications less effective, ineffective, or possibly even harmful over time. Patients were introduced to why mind, body, and behavioral methods of pain control are part of a comprehensive pain management package.

Session 2: "Lifestyle and Balance". This session discussed importance of healthy behaviors (e.g. exercise, sleep, caffeine, nutrition, alcohol, tobacco, and emotional health), and how they are related to chronic pain. This session provided interactive education on the stress response of the autonomic nervous system and how pain activates the stress response, thereby providing rationale for why learning how to

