*Self-referral.* Fliers advertising the study were available in the clinic lobby. Interested patients could respond to the information on the study flier by calling a designated study phone number. The research

staff telephoned interested patients, using an IRB-approved telephone screening script, conducted a brief screening survey and invited eligible patients to participate.

**Informed consent and baseline appointment.** For patients who were eligible and agreed to participate, the research staff scheduled a one-hour, in-person appointment at the medical center at the patient's convenience. At the appointment, the research staff explained the study, invited the patient to participate, and obtained informed consent, using an IRB-approved recruiting script. Informed consent included access to patient medical records for research, including pharmacy and utilization of medical, mental health and chemical dependency services. The Research Associate answered all questions by the patient about the study, and reviewed the study consent form with the patients. If the participant stated that they understood the purpose of the study, and agreed to participate, the participant's signature was obtained. The research staff also clearly explained the HIPAA authorization form, and obtained the participant's signature.

After signing the consent form, the patient was asked to complete the online baseline survey, using a study laptop. The survey took about 45-60 minutes to complete.

**Randomization.** Randomization was conducted independently, using a block randomization approach and a SAS random-number generator. Assignments were pre-determined and placed in sealed opaque envelopes. As each eligible patient provided informed consent, the research staff opened an envelope to identify the treatment group to which the patient was assigned. Assignments were concealed from study staff until opened in front of patient.

Participants assigned to the intervention arm were required to attend their first session within 3 months of completing the baseline survey. In situations where this was difficult, participants were offered the option to re-do the baseline survey or forgo the group sessions and proceed with the remainder of the study (the 6 and 12 month follow up telephone interviews), which aligned with the planned intent-to-treat analysis of the study.

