**Follow-up appointments.** Patients were interviewed by telephone at 6 and 12 months post intake. Trained DOR interviewers conducted follow up interviews (approximately 45 minutes) using standardized scripts and procedures. For patients who were difficult to reach by phone, we sent contact letters to let them know we were trying to reach them, and provided a telephone number to contact us. The Kaiser EHR was utilized for locating updated contact information. Multiple attempts were made to contact patients over 4-6 week time period.

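### The only adverse-event recognition route described depends on staff contact, which is more frequent in PA+UC; an EHR-based safety table by arm would remove that imbalance cheaply

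*Protocol*

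**What the plan says.** Under Study-specific potential adverse events, the protocol states: "The study team members were trained to identify adverse" reactions. It gives no adverse-event question, form, recall window or record search.

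Under Safety monitoring plan and reporting mechanisms, it provides for an Independent Safety Monitor (ISM) "who periodically examined aggregate reports of adverse events generated by the primary data analyst". The twice-yearly report is to summarise all events, serious or not, and their relationship to the intervention. Whether it is split by arm is not stated.

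Scheduled contact differs by arm. In PA+UC, "The intervention consists of 4 group sessions, one meeting per week, led by a licensed psychologist trained in pain management". In both arms, "Patients were interviewed by telephone at 6 and 12 months post intake".

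The Significance section names the harms of concern in this population: "Increases in adverse events such as opioid abuse, falls, overdose and deaths associated with COT". Under Health Care Utilization and Engagement, "acute care services (number of emergency room visits and inpatient stays) within KPNC were extracted from the EHR". Consent to record access is wide, "including pharmacy and utilization of medical, mental health and chemical dependency services". No section connects these records to the safety reports.

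**The concern.** If events come to light mainly when staff talk to patients, the chance that an event is recorded depends on the arm. A higher count in PA+UC could then reflect more contact, and similar counts could hide a true difference. The report to the ISM also asks for relatedness to the intervention, a judgement made on whatever events reach it.

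A second problem does not depend on the arm. Once the sessions end, contact is limited to the two interviews. An overdose, a serious fall or a death between contacts may not reach staff, and a patient who has died cannot report anything. Aim 3 asks whether the intervention changes opioid use, so these are events a reader will want to see by arm.

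**Working it through.** The protocol gives no adverse-event rate or detection figure to reproduce. The check is how far unequal contact could distort counts when true risk is equal.

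**Inputs from the protocol**
- PA+UC: 4 weekly sessions; first session due within 3 months of baseline; patients could forgo sessions (Randomization).
- Both arms: 2 telephone interviews, at months 6 and 12.
- 376 randomized, 342 followed at 12 months (Sample Size).

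**Assumptions (not in the protocol)**
- Each contact reveals an earlier event independently with probability q, the same for a session as for an interview.
- The session leader counts as study personnel.

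**Step 1: contact ratio.** (4 + 2)/2 = 3.0 with full attendance. With 0, 1, 2 or 3 sessions attended it is 1.0, 1.5, 2.0 or 2.5.

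**Step 2: upper bound on detection.** If all contacts fall after the event, the ratio is [1 − (1 − q)^6] / [1 − (1 − q)^2].

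| q | PA+UC : UC |
|---|---|
| 0.01 | 2.94 |
| 0.10 | 2.47 |
| 0.25 | 1.88 |
| 0.50 | 1.31 |
| 0.90 | 1.01 |

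This applies only to events before the first session. A session held early in the year cannot reveal a later event.

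**Step 3: allow for timing.** Let events fall evenly over 12 months and count only contacts after the event. UC has two contacts remaining in the first half-year and one in the second, so its detection is 0.5 × [1 − (1 − q)^2] + 0.5 × q.

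Worked case: q = 0.25, first session at month 3 (the latest allowed), sessions 7/30.4 = 0.230 months apart.
- UC: 0.5 × 0.4375 + 0.5 × 0.25 = 0.344.
- Extra detection in PA+UC, events before month 3: (3/12) × (0.75^2 − 0.75^6) = 0.25 × 0.3845 = 0.0961.
- Extra detection between sessions: (0.230/12) × (0.3252 + 0.2461 + 0.1406) = 0.0137.
- PA+UC: 0.344 + 0.110 = 0.454. Ratio 0.454/0.344 = 1.32.

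| First session | q = 0.01 | q = 0.25 | q = 0.50 | q = 0.90 |
|---|---|---|---|---|
| Month 1 | 1.29 | 1.13 | 1.05 | 1.00 |
| Month 3 | 1.72 | 1.32 | 1.11 | 1.00 |

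**Step 4: completeness.** In the worked case about 66% of events in UC and 55% in PA+UC would go unrecorded. In addition, 376 − 342 = 34 patients (9.0%) were not followed at 12 months.

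**Step 5: common source.** With one EHR extraction, the same window and the same definitions in both arms, the expected detection ratio at equal true risk is 1.0.

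**The case against.** The strongest reply has four parts.

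- **No between-arm safety comparison is planned.** The aims contain no safety aim, and the monitoring section describes periodic review of events and their relatedness. This stands. A reader might infer that a planned comparison is biased; the protocol supports only the conditional statement that such a reading would be open to bias.
- **Staff contact is not said to be the only route.** The reports were generated by the primary data analyst, and a data analyst on the study also retrieved EHR data. A safety monitoring plan, not shown, may say more. This also stands: staff recognition is the only route described, which does not prove it was the only one used. Nor can it be said that overdoses, falls or deaths were kept from the ISM, because the report was to cover all events.
- **Arm-neutral data already exist.** Aim 2c compares acute care use by arm, opioid dispensing comes from the EHR, and misuse is measured with SOAPP and COMM. This stands in part. The acute-care data are named as counts without cause, and falls, overdose and death are not named as items to extract.
- **The statement on physical risk is not a contradiction.** A reader might set "This study entailed no physical procedures and imparted no physical risk" against the harms in the Significance section. The first concerns the study's own procedures, and the study prescribed no drugs; the second concerns background harms of long-term opioid therapy. They are compatible, and no rewording is needed.

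What remains is that the one method described depends on arm, while a neutral source covered by consent was available.

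**Conclusion.** The point holds as a cheap improvement. The described recognition route gives PA+UC up to three times the scheduled contacts of UC. It would be wrong to read that 3:1 as the factor by which events are over-recorded: it is a contact ratio under full attendance and an upper limit. For events spread evenly over the year, the detection ratio is about 1.0 to 1.7. It lies toward the upper end only if each contact is unlikely to reveal an event and the sessions start late, and lower attendance reduces it further.

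These ratios rest on an assumed q, independence between contacts, equal yield from a group session and an interview, and even event timing. None of these comes from the protocol, and the model does not apply to deaths. The direction, more recording in PA+UC, follows from the contact schedule if staff recognition was the working route. No efficacy result is affected.

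**What to change.** State how adverse events were ascertained. Then, over the same 12 months from randomization and by randomized arm, tabulate from the EHR:

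- all emergency visits and all inpatient stays;
- those coded for overdose or opioid poisoning, and for falls or injury;
- deaths;
- new chemical dependency treatment.

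Use the same definitions in both arms. Provide the table to the ISM or, as follow-up is complete, report it as the between-arm safety summary. List staff-noticed events separately, marked as unequally ascertained.

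**Cost.** A modest additional extraction of diagnosis codes and deaths, with event definitions to be written; the visit counts are already extracted and consent covers the utilization records. Care outside KPNC is seen only through the survey, and most events in the table will be unrelated to the intervention.

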### **QUALITATIVE INTERVIEWS**

Over the course of the study, we interviewed 13 primary care physicians about their experience caring for patients on prescription opioids. Through a series of open-ended questions, we solicited feedback on the current prescribing environment and how it has affected providers' relationships with patients, and the quality of care provided. The interviews were conducted by the study research clinician. All interviews were conducted during lunch hours at the primary care clinic, and were recorded. Audio files were transcribed, and summaries were drafted of each interview. Data will be used to supplement main quantitative findings.

**[name], Data Analyst**. [name] primary responsibilities on the study were compiling final study results, and drafting methods and results for final research report and manuscripts. She cleaned survey data, retrieved relevant data from EHR and compiled final data tables. She created summary statistics for outcome variables, and compared differences between treatment groups on outcome measures at 6 and 12 months. She ran cross-sectional multivariate models to examine relationships between the outcomes and the two treatment arms at the 6-month and 12-month follow-ups, and used a repeated measures mixed effects framework to examine differences in outcomes by treatment arm over time.
